2.2 STUDY DESIGN

A brief summary of the main study design features and assessments to be performed is presented here. Refer to Section 3 of the study protocol for complete details.

This is a Phase 2b, multi-center, double-blind, placebo-controlled parallel group, dose range finding study of once daily bexagliflozin tablets in either treatment-naïve type 2 diabetes subjects or subjects previously treated with one OHA. Treatment-naïve subjects are those who have never received prescription anti-diabetic medications or who have received no more than 14 days of prescription medications for diabetes in the 12 weeks prior to enrollment. Subjects who meet all of the inclusion criteria, none of the exclusion criteria and who consent to participate in the study are eligible to be enrolled to complete a 6 to 10 week washout (only required if the subject is not treatment naïve), and a 2 week placebo run-in period prior to being randomized. Subjects who can adhere to the run-in medication dosing scheduled (i.e., miss no more than one dosage in 2 weeks) and who have HbA1c between 7 and 8.5% at baseline will be eligible for randomization. Eligible subjects will be randomized to receive oral bexagliflozin tablets, 5, 10, 20 mg or placebo, once daily for 12 weeks in an outpatient setting. Subjects will visit their study site at weeks 2, 6 and 12 for safety and efficacy evaluation, with a follow up visit at week 14.

2.2.1 Number of Subjects

Approximately 320 subjects will be randomized into this study, with approximately 80 subjects in the placebo group and 80 subjects in each of the three bexagliflozin treatment groups (5 mg, 10 mg and 20 mg).

The study will be conducted at multiple investigative sites and will likely involve variable numbers of subjects at each site. Enrollment will be on a competitive basis but each site will be capped at 32 subjects. Activation of investigational sites will be centrally controlled by interactive web response system (IWRS). Subject randomization will be deactivated for all sites when the planned number of subjects is met. However, if a potential subject is in the washout period and wishes to participate in the study, the subject will be allowed to continue and, if eligible, to be randomized.

2.2.2 Randomization and Blinding Procedures

Eligible subjects, who sign the informed consent form (ICF), complete the run-in period and meet all inclusion/exclusion requirements will be randomized in a 1:1:1:1 ratio on Day 1 (Visit 1 – Treatment Phase) to receive investigational product according to a computer-generated randomization schedule. Subjects will be assigned to treatment groups in sequential order as they qualify for the study, using a centrally located and managed IWRS. Randomization will be stratified according to background anti-diabetic treatment status (treatment naïve or taking one OHA). Upon randomization, each subject will receive a subject randomization number and a drug kit assignment.

This is a double-blind, placebo-controlled study. The sponsor, investigators, study coordinators, pharmacists, study subjects and the cardiovascular adjudication committee members will be blinded to the study medication. To maintain blinding of the individual treatment assignment, the results of urinary glucose testing will not be made available to any study personnel or subjects.

If knowledge of the treatment is needed to manage the subject's condition, the investigator will contact the IWRS to obtain the treatment assignment. If unblinding occurs for any reason, the time and reason for breaking the blind will be recorded on the electronic case report form (eCRF) and the sponsor must be notified within 24 hours.

A designated statistician who is not involved with the study operation will hold the treatment codes. The unblinded treatment information can be provided to the Data Safety Monitoring Board (DSMB) to facilitate the evaluation of any clinically important increase in the rate of a serious suspected adverse reaction or to the designated safety contact when the treatment information is required to determine if an expedited safety report must be submitted to regulatory agencies.

The treatment assignment will continue to be withheld from the cardiovascular adjudication committee members until all global investigational studies are completed and a meta-analysis to assess cardiovascular risk is conducted.

2.2.3 Efficacy Assessments

Efficacy assessments will include blood draws for a glycemic control laboratory panel, including HbA1c and FPG, body weight, and systolic and diastolic blood pressure (BP).

Blood samples for HbA1c and FPG will be obtained at Screening (Visit S1), Run-in (Visit S5), Treatment Period Visits 2, 3, 4 and Follow-up Visit 5. Body weight will be measured at Screening (Visit S1), Washout (Visit S2), Run-in (Visit S5), Treatment Period Visits 2, 3, 4 and Follow-up Visit 5. Supine, sitting and standing

BP measurements will be obtained at Screening (Visit S1), Run-in (Visits S4 and S5), Treatment Period Visits 2, 3, 4 and Follow-up Visit 5.

2.2.4 Safety Assessments

Adverse event (AE) occurrences will be recorded throughout the study. For non-serious AEs, documentation will start from the time the subject signs the ICF until the last scheduled contact. For serious adverse events (SAEs), documentation will start from the time the subject signs the ICF through 14 days after the last treatment, or for ongoing events, until the event is resolved or the subject is lost to follow-up. Careful evaluation and documentation of the following potential adverse events of special interest, as outlined in Sections 6.10.6 through 6.10.9 of the Protocol, will also occur throughout the study: urinary tract infections (UTIs), genital mycotic infections (GMIs), hepatotoxicity and hypoglycemia.

A complete physical examination will be performed at Screening (Visit S1) and at the Follow-up Visit 5. Unless clinically indicated, an abbreviated physical examination will be performed at Run-in (Visit S5) and Treatment Period Visit 4. Vital sign measurements (supine, sitting and standing blood pressure, pulse, temperature and respiratory rate) will be performed at Screening (Visit S1), Run-in (Visits S4 and S5) and Treatment Period Visits 2, 3, 4 and Follow-up Visit 5. A 12-lead electrocardiogram (ECG) will be conducted at Screening (Visit S1), Run-in (Visit S5), Treatment Period Visit 4, Follow-up Visit 5 and whenever clinically indicated. ECG measurements include RR interval, PR interval, QRS duration, QTcB, P wave axis and QRS axis, overall interpretation. Each ECG should also be assessed by the investigator for signs of ischemia, clinically significant hypertrophy, and clinically significant T-wave abnormalities.

Clinical laboratory tests, including hematology, serum chemistry and electrolytes, lipids, infectious disease testing, urine drug screen, urinalysis and urine pregnancy test [women of childbearing potential (WOCBP) only], will all be obtained at Screening (Visit S1). Hematology, serum chemistry and electrolytes samples will also be obtained at Run-in (Visit S5), Treatment Period Visits 2, 4 and Follow-up Visit 5. Serum lipids will be obtained at Run-in (Visit S5), Treatment Period Visit 4 and Follow-up Visit 5. Urinalysis and urine pregnancy test (WOCBP only) will be obtained at Washout (S2), Run-in (Visits S4 and S5), Treatment Period Visits 2, 3, 4 and Follow-up Visit 5.

2.2.5 Other Assessments

Other assessments include concomitant medication use throughout the study and compliance with study drug administration. Compliance is reviewed at each visit after investigational product has been dispensed. In addition, for subjects who fail to

complete the study (through follow-up) or treatment, the reason for study or treatment discontinuation will be recorded.

Blood samples for the population PK analysis will be drawn at Treatment Period Visits 2, 3 and 4.

Table 1. Schedule of Events

Visit number	Screen-ing	Washout		Run-in		Treatment				Follow Up
	S1	S2	S3	S4	S5	V1	V2	V3	V4	V5
Time to Randomization (weeks) ¹	up to 15 weeks	-12 or -8	-10 or -6	-2	-0.5	0	2	6	12	14
Informed Consent	X									
Screening for I/E criteria	X	X			X					
Demographics and medical history	X									
Diet & exercise counseling ²		X		X						
Physical exam ³	X				X				X	X
Body weight	X	X			X		X	X	X	X
Diary & glucometer record review ⁴			X	X	X	X	X	X	X	X
Start washout		X								
Dispense Run-in Medication				X						
Randomization						X				
Vital signs	X			X	X		X	X	X	X
ECG	X				X				X	X
Dispense study medication ⁵						X				
Blood draw for clinical lab test ⁶	X				X		X	X	X	X
Population PK sampling							X	X	X	
Urine collection ⁷	X	X		X	X		X	X	X	X
AE		X	X	X	X	X	X	X	X	X
Con Med		X	X	X	X	X	X	X	X	X

¹ Screening period may last up to 3 weeks; washout period will be 10 weeks for subjects on a TZD or 6 weeks for subjects on other OHA, which includes a clinic visit (S2) and a phone interview (S3); run-in period is to be 2 weeks (S4 to S5); the treatment period (V1 to V4) will be 12 weeks. A visit window of ± 3 days is allowed for all visits except visit V1. Visit V1 is to be scheduled at 3 days after visit S5 and can be extended to 5 days pending on HbA1c value availability.

² Counseling will be performed at S2 for washout and at S4 for treatment naïve subjects.

³ A complete physical examination will be performed by the investigator at screening (S1) and at the termination visit (V5). Abbreviated physical examinations will be performed by the investigator at all other time points, unless clinically indicated. General assessment of the skin, heart, lungs and abdomen will be performed.

⁴ Glucometer and diary will be dispensed to each enrolled subject at visit S2 (for subjects undergoing washout) or S4 (for subjects not undergoing washout), and subjects will be trained in glucometer use and SMBG recording. The SMBG record will be reviewed by the investigator at all subsequent visits.

⁵ At visit V1, an investigational product kit will be dispensed; subjects should bring in their study medication to be checked on visits V2, V3, and V4.

- ⁶ *Blood sample collection and laboratory tests at designated visits are listed in Appendix 2 of the Protocol. A minimum fasting time of 10 h must be confirmed prior to blood draw.*
- ⁷ *UPT is scheduled for all women at screening and for WOCBP thereafter.*

3 STATISTICAL METHODS

3.1 General Methods

3.1.1 Computing Environment

All statistical analyses will be performed using SAS® Version 9.4 or higher.

3.1.2 Reporting of Numerical Values

All clinical study data will be presented in subject data listings. Data summaries will use descriptive statistics (number of subjects [n], mean, standard deviation [SD], first quartile [Q1], median, third quartile [Q3], minimum and maximum) for continuous variables, and frequency and percentage for categorical and ordinal variables. If there are missing values, the number of missing will be presented, but without a percentage.

Means, medians and confidence intervals (CIs) will be reported to one decimal place more than what is reported on the eCRF or by the laboratory/vendor. Standard deviations will be reported to two decimal places more than what is reported in the data. Interquartile range values (Q1 and Q3) and minimum and maximum values will be reported to the same number of decimal places displayed on the eCRF or by the laboratory/vendor.

P-values will be reported to four decimals.

3.1.3 Significance Level

Inferential treatment comparisons on efficacy endpoints will be declared statistically significant at the 0.050 level using two-tailed tests. There will be no adjustments made for multiple comparisons. Tests for interaction will be declared statistically significant at the 0.100 level.

All confidence intervals will be two-sided 95% CIs.

3.1.4 Multiplicity

The primary objective of this study is to identify the effect of bexagliflozin tablets in three strengths on the placebo-corrected change from baseline in HbA1c after 12 weeks of treatment. All secondary endpoints are considered exploratory and adjustment for multiple endpoints and multiple comparisons within each endpoint will not be performed.

3.1.5 Baseline and Change from Baseline

Baseline is defined as the last non-missing value obtained immediately prior to administration of the first dose. For each post-baseline value, change from baseline will be calculated by subtracting the baseline assessment value from the post-baseline assessment for each subject (i.e., post-baseline assessment – baseline assessment).

3.1.6 Study Day

Subjects will be randomized and the first dose of investigational product during the Treatment Period will be considered Day 1. Study day for event dates prior to randomization and first dose will be determined as Study Day = (Event Date – Treatment Period First Dose Date). Study day for events after randomization and treatment period first dose will be determined as Study Day = (Event Date – Treatment Period First Dose Date) + 1.

3.1.7 Handling of Missing/Incomplete Values

To the extent possible, attempts will be made to minimize the amount of missing data through measures planned in the study conduct. However, if missing data are present for the primary efficacy endpoint, HbA1c, they will be handled using a multiple imputation approach, as a part of a sensitivity analysis, as described in Section 3.8.1 of the SAP. For all other endpoints, the missing data will not be imputed and only the observed data will be used for analyses. The number, timing, pattern, reason for and possible implications of missing values in efficacy and safety assessments will be investigated. The dropout patterns may be assessed by graphical methods (e.g., Kaplan-Meier plot for time to drop-out).

Rules for handling missing dates are outlined within applicable sections.

3.1.8 Methods of Pooling Data

Pooling of subjects from different study centers may be done to ensure a sufficient number of subjects per treatment arm for analyses that include study center as a model effect. Therefore, pooling will be done in the case where there is at least one study center with fewer than 5 subjects in the per protocol analysis set per treatment arm. Study centers will be pooled based on geographical region (i.e., closest geographical site) within each country. Study center pooling will be determined during a blinded review of the data prior to database lock.

3.1.9 Analysis Visit Windows

Visit windows for study conduct are specified in footnote 1 of Table 1: Schedule of Events. Treatment period visits are planned for Day 1, Randomization (V1: Week 0),

Day 15 (V2: Week 2), Day 43 (V3: Week 6) and Day 85 (V4: Week 12). There is also a scheduled follow-up visit at Day 99 (V5: Week 14). A visit window of ± 3 days is allowed for all visits except for Week 0. Week 0 (Study Day 1, Randomization) is to be scheduled at 3 days after the last run-in visit (Visit S5) and can be extended to 5 days pending on HbA1c value availability.

For any unscheduled visits, Table 2 will be used to map the unscheduled assessments to the analysis visits prior to selection of records for analysis

Table 2: Nominal (Targeted) Time Points and Analysis Visit Windows

Assessment	Nominal (Targeted) Time Point	Analysis Visit Window (Interval in Study Days)
Baseline Assessments	Week 0 (Study Day 1)	\leq Day 1
Post-Baseline Assessments	Week 2 (Study Day 15)	Day 8 through Day 22
	Week 6 (Study Day 43)	Day 36 through Day 50
	Week 12 (Study Day 85)	Day 78 through Day 92
	Week 14 (Study Day 99)	Day 93 through Day 105

After mapping the data to the analysis visits, the following rules will apply unless otherwise specified for a particular analysis:

- If multiple records are available within a single analysis visit window, the record closest to the planned assessment day will be selected for analysis.
- If 2 records are equidistant from the target day, then the first record will be selected.
- If a subject has no record in an analysis window, the subject will be considered missing at that time point.

For subjects withdrawing early, the end of study data (early termination visit) will be mapped according to the analysis visit windows in Table 2 for summarization and analysis. However, if the visit does not fall within any of the analysis visit windows then the visit will be mapped to the next scheduled time point.

3.2 Analysis Populations and Subgroups

3.2.1 Definition of Analysis Populations

All Enrolled

All subjects who signed an informed consent form will be included in the all enrolled analysis set.

Full Analysis Set

All subjects who are randomized, take at least one dose of double-blind study medication, and have at least one post-randomization HbA1c measurement will be included in the full analysis set. All analyses of the full analysis set will be based on each subject's randomized assigned treatment.

Intent-to-Treat Analysis Set

All subjects who are randomized will be included in the intent-to-treat analysis set. All analyses of the intent-to-treat analysis set will be based on each subject's randomized assigned treatment.

Safety Analysis Set

All subjects who are randomized and take at least one dose of double-blind study medication will be included in the safety analysis set. Safety analyses will be based on the medication that was actually dispensed to each subject.

Per Protocol Analysis Set

The per protocol (PP) analysis set will include all subjects in the full analysis set who meet the study eligibility requirements as defined in Section 4 of the study protocol and have no major protocol deviations that affect the validity of the efficacy measurements. All analyses of the per protocol analysis set will be based on each subject's randomized assigned treatment. Major protocol deviations are defined as:

- Study drug compliance <80%
- Missing baseline or Week 12 HbA1c measurement
- Received prohibited medication including SGLT2 inhibitor, insulin or GLP-1 receptor agonists
- Randomization error
- Inappropriate unblinding (i.e., blind was broken (requested in IWRS) in absence of medical emergency or blind broken by unauthorized site personnel)
- Subject was dispensed with incorrect study medication

Subject exclusions will be determined on a case-by-case basis during a blinded review of the data prior to database lock. In addition, a blinded review of concomitant medications will be performed to further identify any other potential restricted medications.

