Rescue medication for hyperglycemia should be prescribed by the investigator at any time it is deemed necessary for the well-being of the subject. During the 12 week treatment period, a review of diet and exercise counseling is suggested prior to prescription of rescue medication in the absence of specific medical indications for rescue medication. Rescue medication is suggested if, after a review of diet and exercise counselling:

1. more than 3 consecutive, daily, fasting SMBG measures are ≥ 270 mg/dL (15 mmol/L) from week 1 to week 6, or ≥ 240 mg/dL (13.3 mmol/L) from week 6 to week 12
2. fasting SMBG values are ≥ 250 mg/dL (13.9 mmol/L) and associated with clinical signs or symptoms of hyperglycemia (e.g. weight loss, blurred vision, increased thirst, or increased urination, or fatigue), and the signs or symptoms are severe

The investigator may provide rescue treatment with any approved medication for diabetes that is not otherwise contraindicated, with the exception of an SGLT2 inhibitor, as study subjects may already be taking a drug in that class as a consequence of being randomized to receive bexagliflozin.

Subjects who receive rescue medication due to poor glycemic control will continue to receive investigational product and standard of care per investigator decision, according to current treatment guidelines. Following the exit visit subjects will be advised to see their primary physician to undergo treatment to control their diabetes.

If hypoglycemia occurs in any subject prescribed rescue medication for hyperglycemia during the study, the total daily dose of the rescue medication should be reduced 50% or more at the discretion of the investigator.

OTHER SAFETY MONITORING ACTIVITIES

The safety monitoring activities will include assessment of vital signs, physical examinations, urinalysis, blood chemistry, hematology, adverse events, and concomitant medication use. The occurrence of blood, liver, or skin disorders will be monitored through laboratory testing and evaluation of adverse event documentation.

Adverse events of special interest as defined in the statistical analysis plan will include any clinical signs and symptoms that indicate adverse experience in the categories listed below. All such events must be appropriately documented within source documentation.

- Genital mycotic infections
- Urinary tract infections including urosepsis and pyelonephritis
- Diuretic effects including hypovolemia
- Hypotension episodes
- Hepatotoxicity

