4.3 Exclusion Criteria

Subjects who exhibit any of the following characteristics will be excluded from the study:

1. A diagnosis of type 1 diabetes mellitus or maturity-onset diabetes of the young (MODY)
2. Current use of parenteral therapy for treatment of diabetes (insulin or glucagon-like peptide-1 (GLP-1) receptor agonist therapy)
3. Pregnancy or current breastfeeding status
4. Hemoglobinopathy or carrier status for hemoglobin alleles that affect HbA1c measurement
5. Genitourinary tract infection (e.g. urinary tract infection, vaginitis, balanitis) within 6 weeks of screening or history of ≥ 3 genitourinary infections requiring treatment within 6 months of screening
6. Estimated glomerular filtration rate (eGFR), as calculated by the modification of diet in renal disease study equation (MDRD), < 60 mL/min/1.73 m² at screening ([Appendix 2](#))
7. Uncontrolled hypertension (average of two sitting measurements of systolic blood pressure > 160 mmHg or diastolic blood pressure > 95 mmHg) at screening
8. A positive result on hepatitis B surface antigen (HBsAg), hepatitis C (HCV), or positive result from screen for drugs of abuse
9. History of human immunodeficiency virus (HIV) infection
10. Life expectancy < 2 years
11. History of New York Heart Association (NYHA) Class 4 heart failure within 3 months of screening
12. History of MI, unstable angina, stroke, or hospitalization for heart failure within 3 months of screening
13. History of treatment with an investigational drug within 30 days or within 7 half lives of the investigational drug, whichever is longer
14. Previous treatment with bexagliflozin or EGT0001474
15. Currently or within 6 months of taking any SGLT2 inhibitors from screening
16. Currently participating in another interventional trial
17. Not able to comply with the study scheduled visits
18. Affected by any condition, disease, disorder, or clinically relevant abnormality that, in the opinion of the investigator, would jeopardize the subject's appropriate participation in this study or obscure the effects of treatment
19. ALT or AST ≥ 2.5 x upper limit of normal (ULN) or total bilirubin ≥ 1.5 x ULN with the exception of isolated Gilbert's syndrome at screening

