5.7 Restrictions

5.7.1 Prior Therapy

All subjects will continue regimens for medical conditions other than diabetes during the study as indicated above. No subject shall have been treated with an investigational drug within 30 days of screening or within a period equal to less than 7 half-lives of the investigational drug, whichever is longer. No subject shall have been treated with an SGLT2 inhibitor within 6 months of screening. Subjects taking insulin or GLP-1 receptor agonists are not eligible for this study.

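### The per-protocol definition lists insulin and GLP-1 receptor agonists as prohibited with no rescue exception, although the protocol permits both as rescue during treatment

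*SAP*

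**What the plan says.** **Per-protocol set (SAP 3.2.1).** Members are full-analysis-set subjects who meet the eligibility criteria and "have no major protocol deviations that affect the validity of the efficacy measurements". The listed major deviations include "Received prohibited medication including SGLT2 inhibitor, insulin or GLP-1 receptor agonists" and "Missing baseline or Week 12 HbA1c measurement". The section then adds: "Subject exclusions will be determined on a case-by-case basis during a blinded review of the data prior to database lock". A blinded look at concomitant medication is to find any further restricted drugs. Nothing is said about rescue.

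**Rescue (protocol 3.2.3 and 5.6).** "The investigator may provide rescue treatment with any approved medication for diabetes that is not otherwise contraindicated, with the exception of an SGLT2 inhibitor". Treatment is not stopped: "Subjects who receive rescue medication due to poor glycemic control will continue to receive investigational product". Section 5.6 classes anti-diabetic drugs given for hyperglycemia as rescue and excludes no class.

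**Restrictions on the two classes (protocol 4.3 and 5.7.1).** Both concern entry. Exclusion criterion 2 is "Current use of parenteral therapy for treatment of diabetes (insulin or glucagon-like peptide-1 (GLP-1) receptor agonist therapy", and the section on prior therapy states: "Subjects taking insulin or GLP-1 receptor agonists are not eligible for this study".

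**Related rules.** SAP 3.6 counts hyperglycemia treatment as rescue only from 2 weeks' duration. SAP 3.8.1 treats HbA1c after rescue as missing in the primary model and repeats that model in the per-protocol set. SAP 3.1.8 uses per-protocol counts per center and arm to trigger center pooling.

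**The concern.** Two of the three classes the SAP calls prohibited are allowed by the protocol after randomization. A subject whose investigator followed the protocol can therefore be listed as a major deviator.

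Rescue is a response-related event. If the drug works, it should be more frequent on placebo, and rescued subjects are those with the highest HbA1c. Removing some of them because of the drug the investigator chose is selection on outcome, and it pulls the per-protocol difference toward zero. Part of any gap between the full-analysis-set and per-protocol results would then reflect the choice of rescue drug and not adherence.

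**Working it through.** **1. The plan's own figure.** Protocol 9.2 assumes a difference of 0.5, SD 0.9, two-sided 5% and 70 evaluable per arm. The noncentrality is 0.5 / (0.9 × √(2/70)) = 0.5 / 0.152 = 3.29 on 138 degrees of freedom, and the noncentral t gives power 0.904. The stated 90% or so reproduces, and the concern does not touch it. With 80 per arm, the scale used below is SE = 0.9 × √(2/80) = 0.142.

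**2. Whom the clause catches.** Take a subject treated for hyperglycemia as the protocol permits and measured at Week 12. The result depends on whether a post-rescue Week 12 value counts as present for the Week 12 criterion.

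| Treatment given | Value counts as present | Value counts as missing |
|---|---|---|
| Oral drug, 2 weeks or longer | stays | leaves (a) |
| Insulin or GLP-1 agonist, 2 weeks or longer | leaves by default | leaves |
| Oral drug, under 2 weeks | stays | stays |
| Insulin or GLP-1 agonist, under 2 weeks | leaves by default | leaves by default |

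(a) Unless the pre-rescue sample required by protocol 3.2.3 falls in Days 78 to 92, the Week 12 window of SAP Table 2; the Week 12 value is then not missing.

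For SAP-defined rescue, the contrast by class thus needs the left-hand reading, apart from case (a). For short courses it holds under both, because those values are not post-rescue under SAP 3.6.

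**3. Size under the left-hand reading.** The documents give neither rescue rates nor drug shares, so both are assumptions shown as a range.

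- From protocol 9.2: placebo versus 20 mg, 80 per arm, Week 12 difference -0.50, SD 0.9.
- Assumed: baseline normal (mean 7.75, SD 0.45) clipped to 7.0–8.5; SD of change 0.35, 0.65, 0.90 and mean differences -0.15, -0.38, -0.50 at Weeks 2, 6, 12; correlations 0.65 (2–6), 0.50 (2–12), 0.80 (6–12).
- Assumed rescue: it occurs in an interval if the mean of the two adjacent HbA1c levels plus N(0, 0.4) noise exceeds a threshold. Thresholds were set to give placebo rates of 1, 3, 5, 10 and 15%; the same thresholds give 0.25, 0.9, 1.8, 4.1 and 6.8% on active. HbA1c stands in for the protocol's self-monitored glucose triggers.
- Model: visit, treatment-by-visit, baseline, unstructured covariance, maximum likelihood; post-rescue values missing; no other dropout. In each of 10,000 replicates, keeping everyone is compared with deleting a random share of rescued subjects.

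Central case: placebo rescue 10%, active 4.1%, 40% of rescues with insulin or a GLP-1 agonist, default always applied.

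- Deleted: 80 × 0.10 × 0.40 = 3.2 placebo and 80 × 0.041 × 0.40 = 1.3 active subjects.
- Estimate: -0.478 with everyone kept, -0.461 after deletion. Shift 0.017, or 0.017 / 0.142 = 0.12 SE. The starting value is not -0.50 because rescue depends partly on values that are then missing.

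| Share of rescues deleted (10% placebo rescue) | 10% | 20% | 25% | 40% | 60% |
|---|---|---|---|---|---|
| Shift toward zero | 0.0040 | 0.0083 | 0.0102 | 0.0166 | 0.0254 |

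The 20% column is also the central case with half of the subjects kept by the blinded review. Over placebo rescue of 1% to 15% and shares of 10% to 60%, the shift is 0.001 to 0.030 (0.030 / 0.142 = 0.21 SE). With a weaker link between HbA1c and rescue (noise SD 0.8), it is 0.001 to 0.021, at most 0.15 SE. The Monte Carlo SE of each shift is at most 0.0005.

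**4. Route to the primary model.** Pooling is triggered if any center has fewer than 5 per-protocol subjects per arm. Protocol 3.1 plans PK sampling at 20 centers, so there are at least 20. For all to reach 5 per arm, 20 × 5 = 100 subjects per arm would be needed, against about 80 planned. Pooling is therefore triggered with or without these few subjects.

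**The case against.** The strongest defense is that SAP 3.2.1 already has a remedy. Exclusion is limited to deviations that affect the efficacy measurements and is decided subject by subject under blind, so reviewers may rule that permitted rescue is not prohibited medication; the shift is then 0. This stands as a limit on the consequence. It does not remove the conflict: the section gives reviewers no criterion for permitted rescue, and the added medication review looks for further drugs, not for drugs to strike off. Nor can the bullet be confined to entry breaches, since eligibility is a separate condition of the same set and the words would be largely redundant.

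It is also fair that no rescue rate is documented, that nothing shows 10% rescue with a 40% share to be typical, and that the bias is conservative in an analysis with no decision rule attached. These points keep the severity low.

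Four stronger inferences are tempting and not supported:

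- *Such subjects will be excluded.* Exclusion is only the written default.
- *Every subject rescued before Week 12 leaves if post-rescue values count as missing.* A pre-rescue sample in Days 78 to 92 supplies a Week 12 value. For the same reason, the title of SAP Table 14.2.1.2.6, which drops post-rescue HbA1c in the per-protocol set, does not show which reading was meant: such a subject has a later value to drop.
- *The bias could reach 0.055.* If all rescued subjects left, the same model gives shifts of 0.010 to 0.055, but that comes from the Week 12 criterion and not from this clause.
- *The primary result is biased.* The primary analysis uses the full analysis set and drops post-rescue values whatever the drug. Saying it cannot be touched at all would also be too absolute, because per-protocol counts feed center pooling, but that effect should be negligible.

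**Conclusion.** The conflict between SAP 3.2.1 and protocol 3.2.3 and 5.6 is plain from the text. By the written default, and subject to blinded review, compliant subjects treated with insulin or a GLP-1 receptor agonist for hyperglycemia can be removed from the per-protocol set while those given an oral drug stay. For rescue of 2 weeks or longer, this rests on an unsettled reading of the Week 12 criterion; for shorter courses it does not.

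Confidence is high for the mismatch in wording. The size rests on the assumed rescue rates, drug shares and HbA1c-based trigger: it is a fraction of a standard error across the range examined, toward zero, and nil if reviewers keep these subjects. Severity is minor. The per-protocol sensitivity analysis is what is affected.

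**What to change.** In SAP 3.2.1, limit the bullet to medication the protocol prohibits: an SGLT2 inhibitor at any time, or insulin or a GLP-1 receptor agonist used in breach of the entry criteria or for a purpose other than treating hyperglycemia.

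Add that insulin or a GLP-1 receptor agonist given for hyperglycemia during treatment is handled in the per-protocol set exactly as any other rescue drug:

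- HbA1c after rescue as defined in SAP 3.6 is missing, as in the primary model.
- Courses under 2 weeks are handled as in the primary model.
- The Week 12 criterion is applied in the same way for every drug class.

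The cost is SAP wording before database lock. No new data are needed, because drug names, indications and dates are already reviewed under blind for SAP 3.6. The downside is that the per-protocol set becomes slightly larger and closer to the full analysis set, and keeps subjects with short courses of insulin or a GLP-1 receptor agonist.
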